15.2. E-DIARY COMPLIANCE

The flow of the eDiary entries patient has to follow is:

1. E-RS
2. Study medication compliance
3. Background medication compliance (if applicable)
4. Rescue medication use

Based on this, we can assess if patient has been compliant with their E-RS questions, based on their study medication compliance and therefore no further E-RS compliance needs to be assessed.

15.2.1. DERIVATIONS

E-diary compliance will be calculated as per the following. Use study day assigned to determine the date for each week, as per the windowing conventions described in Section 6.4 of the SAP:

$$\frac{(\text{Week X}^* < \text{number of days study medication data was entered in the e - Diary} \leq \text{Week Y})}{[\text{Study Day at Week Y}] - [\text{Study Day at Week X}] + 1} * 100$$

*If Week X = Day 1, update “<” to be “≤”.

[REDACTED]

[REDACTED]

[REDACTED]

[REDACTED]

[REDACTED]

16. EFFICACY OUTCOMES

16.1. PRIMARY EFFICACY

The primary efficacy analysis will be performed for the mITT population.

16.1.1. PRIMARY EFFICACY VARIABLE & DERIVATION

The primary efficacy variable is change from baseline in FEV₁ AUC_{0-12h} at Week 12. FEV₁ data captured in the eResearch Technology (ERT) database will be used for the model in determining baseline value and for AUC calculation.

16.1.1.1. AUC_{0-T}

Spirometry (FEV₁) will be performed at Screening and the following time points during, each treatment:

- Day 1: ≤40 minutes pre-dose (2 measurements); 30 minutes, 1, 2 and 4 hours post-dose.
- Week 6 and Week 24: ≤40 minutes pre-dose; 30 minutes, 1, 2 and 4 hours post-dose.
- Week 12: ≤40 minutes pre-dose; 30 minutes, 1, 2, 4, 6, 8 and 12 hours post-dose.
- Early Termination and no Week 12 visit spirometry assessment: ≤40 minutes pre-dose; 30 minutes, 1, 2, 4, 6, 8 and 12 hours post-dose.
- Early Termination but with Week 12 visit spirometry assessment: ≤40 minutes pre-dose; 30 minutes, 1, 2 and 4 hours post-dose.
-

Baseline FEV₁ is the mean of the two measurements taken before study medication on the day of first dosing, i.e. ≤40 minutes pre-dose on Day 1.

The average effect will be calculated as the AUC divided by the length of the time interval of interest (for example, 12 hours for AUC_{0-12h} or 4 hours for AUC_{0-4h}). AUC will be calculated using the trapezoidal method, as follows:

$$AUC = \frac{1}{2} \sum_{i=1}^{n-1} (T_{i+1} - T_i)(C_{i+1} + C_i)$$

Where T_i is the ith time value, C_i is the ith effect value, n is the number of time values. The change from the baseline FEV₁ to average FEV₁ (AUC) will be summarized and analyzed. If two last data points are missing the AUC is set to missing, that is for AUC_{0-12h} we require at least up to 8 hours of assessments and for AUC_{0-4h} we require at least up to 2 hours of assessments. This would mean if we only have 8 hours of assessments, then we would calculate AUC_{0-8h}, however it would still be labelled as AUC_{0-12h}. If there is no pre-dose measurement

available for the calculation of the AUC, then the AUC will not be calculated. The pre-dose measurement used in the calculation of AUC is the latest value measured ≤ 40 minutes pre-dose. The pre-dose value will be used as time 0 when computing AUC_{0-T} .

For AUC_{6-12h} we require at least the 6-hour and 12-hour timepoint for analysis.

16.1.2. MISSING DATA METHODS FOR PRIMARY EFFICACY VARIABLE

The main analysis for the primary endpoint will include estimates from missing data imputation described below. This is done to investigate the influence of missing data due to drop-outs. Only patients with non-missing baseline will be included in the analysis.

The primary analysis will be analyzed using MI based on the missing data assumption Missing at Random (MAR). This process will follow four steps:

1. Partially impute the data for a monotone missing pattern with 100 as a number of imputations and “20905” as seed number. Employ the Markov Chain Monte Carlo (MCMC) method with treatment, region, background medication strata, smoking strata, baseline FEV_1 and average FEV_1 AUC_{0-12h} at Week 12.

1.1 The following SAS codes will be used:

```
proc mi data=<data1> out=<data2> nimpute=100 seed=20905;
  var <treatment> <region> <BackgroundMedStrata> <SmokingStrata>
  <baseline> <visits>;
  mcmc impute=monotone chain=multiple;
run;
```

2. Impute the monotone data using a regression imputation model. Apply by imputation using seed number “20905” with treatment, region, background medication strata, smoking strata, baseline FEV_1 and average FEV_1 AUC_{0-12h} at Week 12.

The following SAS codes will be used:

```
proc mi data=<data2> out=<dataout> nimpute=1 seed=20905;
  by imputation ;
  class <treatment> <region> <BackgroundMedStrata>
  <SmokingStrata>;
  var <treatment> <region> <BackgroundMedStrata> <SmokingStrata>
  <baseline> <visits>;
  monotone regression;
run;
```

3. Each multiple imputed dataset in Step 2 will be analyzed separately, as described in Section 16.1.3 of the SAP.
4. The estimates (LS means, SE, CI, and p-value) from the model analysis in Step 3 will be combined using Rubin’s combination rules for statistical inference.

Sensitivity analysis will be done using:

- Average imputation will be based on data collected on treatment at required visit, or at early termination visit. This will be done on patient level. If there is no such data available, impute with average change from baseline for the particular visit in the opposite randomized treatment group.
- Tipping point approach will repeat the ANCOVA analysis, under Missing not at Random (MNAR) assumption, to assess the robustness of p-value significance. In case the original analysis will produce a p-value<0.05, then the imputed values will be adjusted by a value k (positive) added or subtracted (depending on what worsens the endpoint) to the endpoint of the patients in Ensifentrine group (worsening results) and added or subtracted (depending on what improves the endpoint) from the endpoint of the patients in placebo group (improving results). The value for k is determined by adjusting the bias starting with a value of 0.01 and increasing it with increments of 0.01 until p-value obtained from MI method is no longer statistically significant (p-value>0.05). Seed number used will be the same as for MI analysis, “20905”. If the primary analysis is not significant (p-value>0.05), then the tipping point is reversed by determining value for k by adjusting the bias until p-value≤0.05. If the p-value<0.05 with more improvement in the placebo group comparably to Ensifentrine group, then the tipping point is reversed by adjusting until there will be no more treatment difference between groups.

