7.2.2 Combination of Phone Contact and Reduced Assessments

The site contacts the patient by phone per the SoA (Section 1.3) to complete the following assessments:

- COPD exacerbation
- SAE
- Concomitant medication

In addition, the patient returns to the clinic at Week 24 (and Week 48 if in the Week 48 stratum) to complete the following assessments:

- Spirometry
- SGRQ
- COPD exacerbation
- SAE
- Concomitant medication

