7.3.1 Early Termination/Withdrawal Procedures

If a patient is withdrawn prior to the Week 12 visit, every attempt should be made to have the patient complete the early termination/ withdrawal procedures in the SoA (Section 1.3) as soon as possible.

- If possible, patients should remain on blinded study medication and their maintenance LAMA or LABA medication and ICS (if applicable), follow the withholding procedures prior to Spirometry in Section 8.3.1.2, and should refrain from smoking or caffeinated beverages as recommended in Section 5.4.1.1.
- Patients unable to remain on blinded study medication and/or their maintenance LAMA or LABA medications and ICS (if applicable) should still complete the early termination/ withdrawal visit as soon as possible.

7.3.1.1 12-Hour Spirometry and 1.5 Hour ECG Procedures

For patients who are withdrawn prior to completing the Week 12 visit only, every attempt should be made to have the patient complete the 12-hour spirometry procedures and the ECG procedures at the early termination/withdrawal visit unless consent is withdrawn or the patient is being withdrawn for safety reasons precluding this assessment.

Patients who Continued Blinded Study Medication

Patients who have continued administration of their blinded study medication should complete the spirometry and ECG procedures as follows:

- Spirometry: Pre-dose and 0-12-hour post-dose assessments as per Section 1.4 and Section 8.3.1
- ECG: Pre-dose and 1.5-hour post-dose ECG procedures as per Section 8.4.2.

Patients who Discontinued Blinded Study Medication

Patients who have discontinued blinded study medication prior to the early termination/withdrawal visit may optionally complete spirometry and ECG assessments at the early termination visit if they have not already completed the Week 12 assessments. These patients will not be dosed with blinded study medication. If possible, patients should start spirometry between 6 am and 10am, withhold rescue medication and/or maintenance LAMA or LABA medications for the time period specified in Section 6.7.2, and refrain from caffeinated beverages and/or smoking for the time period specified in Section 5.4.1. The spirometry and ECG procedures should be completed as follows:

- Spirometry: Serial spirometry at 0-hour, 30 min, and 1, 2, 4, 6, 8, and 12 hours.
- ECG: 12-lead ECG at 0-hour and 1.5 hours.

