9.4 Statistical Analyses

9.4.1 Efficacy Analyses

Efficacy analysis will primarily be performed on the mITT population. The primary endpoint and key secondary endpoints will also be evaluated using the PP population as a sensitivity analysis. Impact of imputations and various baseline characteristics will also be checked.

The primary endpoint, change from baseline in FEV₁ AUC_{0-12h} at Week 12, will be compared between treatments using an analysis of covariance (ANCOVA) model adjusting for treatment, region, background medication strata, and smoking status as factors and baseline FEV₁ as covariate. The estimated treatment difference with 95% confidence interval and associated (two-sided) p-value will be presented. Missing data will be imputed to get as close to the mITT population as possible. Primarily imputation will be based on data collected at visits performed after treatment withdrawal or at early termination visits even if outside the visit window. When no such data is available, imputation will primarily be done using multiple imputation based on baseline characteristics and secondarily, as a sensitivity analysis, by the average change in the opposite treatment group as randomized to as a worst-case scenario. Further details on the handling of missing data will be given in the Statistical Analysis Plan.

Key secondary endpoints, FEV₁ AUC_{0-4h}, peak FEV₁, morning trough FEV₁, SGRQ total score and weekly mean E-RS total score, and other continuous secondary or exploratory endpoints will be assessed repeatedly during the study and the change from baseline to pre-specified time point of evaluation will be compared by similar ANCOVA models adjusting for treatment, region, background medication strata and smoking status as factors and baseline as covariate. Data collected at visits performed after treatment withdrawal or at early termination visits will be used in the analyses. Remaining missing data will primarily be imputed using multiple imputation based on baseline characteristics and data collected at post-randomization visits. Since assessed repeatedly, in contrast to primary endpoint, these data will also be analyzed for sensitivity by mixed model repeated measures models with treatment, visit and treatment by visit interaction as factors, baseline as covariate, subject as random factor and covariance structure by visit.

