16.1.3. PRIMARY ANALYSIS OF PRIMARY EFFICACY VARIABLE

The primary objective of this study is to test the hypothesis that there is a difference between ensifentrine in comparison with placebo.

The change from baseline FEV₁ to average FEV₁ AUC_{0-12h} will be compared between ensifentrine and placebo using ANCOVA with fixed effects for treatment, region, background medication strata and smoking strata and baseline FEV₁ as covariate. Missing data will be imputed using imputation described in Section 16.1.2 of the SAP. The estimated treatment difference will be presented with 95% CI and associated p-value. Furthermore, SD will be presented for the treatment difference to check the sample size with 90% power. Summary statistics will be performed on the imputed values.

Model assumptions will be tested as per the following rules on the blinded data, before the DBL.

1. Residual vs Predicted plots will be created to check residuals are uncorrelated and normally distributed.
2. Normality of the data will be checked using Kolmogorov-Smirnov normality test.

If any of the checks specified above fail the test, then alternative approaches will be discussed, including different ways of transposing data. The SAP will be updated to reflect any changes prior to DBL.

Only spirometry measurements with best test review (BTR) grades “Acceptable” and “Borderline Acceptable” are used in the analysis and baseline calculations.

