16.1.4. SENSITIVITY ANALYSIS OF PRIMARY EFFICACY VARIABLE

The primary endpoint will be presented for the following:

- Subgroup analysis will be performed by subgroups, including data imputation described in Sections 7.5 and 16.1.2 of the SAP, respectively.
- Observed data analysis will be performed by the following subgroups:
 - Analysis with no data imputation, including all patients with data collected, on treatment or not, and at required timepoint or at EOS visit (excluding patients with missing data).
 - Analysis with no data imputation, including only patients with data collected at the required visit while still on randomized treatment at scheduled visit, or at end of study visit within the visit window.
- Average imputation, as described in Section 16.1.2 of the SAP.
- Analysis with tipping point approach, as described in Section 16.1.2 of the SAP.
- Analysis with multiple imputation, as described in Sections 16.1.2 and 16.1.3 of the SAP, based on PP population.

[REDACTED]

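### For the overall treatment difference, the primary multiple imputation reproduces the observed-data ANCOVA and leaves other post-randomization FEV1 unused; adding it is a cheap, modest improvement

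*SAP*

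**What the plan says.** **Imputation.** Both steps in SAP 16.1.2 use the same variables: "Employ the Markov Chain Monte Carlo (MCMC) method with treatment, region, background medication strata, smoking strata, baseline". The baseline value is that of FEV1, and the only further variable is the Week 12 average AUC0-12h. The sample code has a `<visits>` placeholder, but the text names only Week 12, and no other scheduled visit has a 12-hour curve. The section also states: "Only patients with non-missing baseline will be included in the analysis".

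**Analysis.** SAP 16.1.3 compares the arms "using ANCOVA with fixed effects for treatment, region, background medication strata and smoking strata and baseline" FEV1.

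**Sensitivity.** The first observed-data item in SAP 16.1.4 is "Analysis with no data imputation, including all patients with data collected, on treatment or not, and at required timepoint or at EOS visit". SAP 16.1.4 also lists an on-treatment analysis, opposite-arm average imputation, a tipping-point analysis and a per-protocol analysis.

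**Data.** SAP 6.4 admits every 12-hour curve to the primary analysis, whenever it was recorded. SAP 16.1.1.1 schedules 0-4 hour spirometry at Day 1, Week 6 and Week 24 as well, and sets AUC0-12h to missing when the last two points are absent.

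**Protocol wording.** For the primary endpoint, 9.4.1 says: "When no such data is available, imputation will primarily be done using multiple imputation based on baseline characteristics and secondarily, as a sensitivity analysis". The sensitivity method it then names is the opposite-arm average. Section 9.4.4 says multiple imputation uses baseline characteristics and post-randomization data, and makes no exception for the primary endpoint. The synopsis still gives the opposite-arm average as the primary choice when no retrieved data exist.

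**The concern.** When the imputation and analysis models share the same covariates and only the outcome is incomplete, imputation adds no information about the treatment difference. SAP 16.1.2 says the imputation is there to examine the influence of dropout. For the overall difference, this model cannot show that influence. A reader who sees the primary result agree with the first no-imputation analysis might be reassured by a match that follows almost entirely from the construction.

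The plan also leaves relevant data aside. The patients concerned have no usable 12-hour curve at any time, but do have FEV1 from another visit or a Week 12 curve too short for AUC0-12h. The protocol allows such patients to arise. One who stops drug before Week 12 and chooses the combined phone and clinic option has reduced clinic follow-up: "the patient returns to the clinic at Week 24 (and Week 48 if in the Week 48 stratum) to complete the following assessments", spirometry included. Someone already off drug "may optionally complete spirometry and ECG assessments at the early termination visit if they have not already completed the Week 12 assessments". For the key secondary FEV1 endpoints, SAP 16.2.2.1 uses all scheduled visits of the parameter, and SAP 16.2.4 makes the baseline-plus-Week-12 model a sensitivity analysis.

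**Working it through.** **1. The plan's own figure.** Protocol 9.2 gives SD 250 mL, 500 vs 300 evaluable patients, a true difference of 59 mL and two-sided 5%.

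- Full-data variance: 250² × (1/500 + 1/300) = 333.33, so SE = 18.26 mL.
- Power = Φ(59/18.26 − 1.96) = 89.8%, which reproduces the stated 90%.

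**2. Equivalence.** Baseline must be present, so Week 12 AUC0-12h is the only incomplete variable. The pattern is already monotone and the MCMC step has nothing to fill. Step 2 draws from the regression that the ANCOVA would fit to the observed patients.

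With a share m missing completely at random, the observed-data variance is 333.33/(1 − m). Rubin's rules split it into 333.33 within imputations and the rest between. At m = 20%:

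- observed-data variance 416.67, SE 20.41 mL;
- between-imputation part 416.67 − 333.33 = 83.33;
- Rubin total with 100 imputations 333.33 + 1.01 × 83.33 = 417.50, SE 20.43 mL;
- expected Monte Carlo noise in the estimate √(83.33/100) = 0.91 mL.

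Simulation (500 vs 300, 100 imputations, 500-600 trials per scenario) agrees. At 20% missing at random, both methods averaged 59.26 mL, with mean SE 20.49 (no imputation) and 20.53 (imputed); the SD of their difference was 0.93 mL. Across the missingness patterns tried, the per-trial correlation was 0.9985-0.9994. The significance call differed in 0.3-2.4% of trials.

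**3. Precision from adding Week 6 FEV1.** Let r be the correlation of Week 6 FEV1 with Week 12 AUC0-12h given the covariates, and q the share of missing patients who have Week 6 FEV1. The documents give neither r, q nor the missing share; all are assumptions.

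Var = 333.33 × [r²/(1 − m(1 − q)) + (1 − r²)/(1 − m)]; power = Φ(59/SE − 1.96).

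| Missing | q | r | SE (mL) | Power |
|---|---|---|---|---|
| 10% | current model | – | 19.25 | 86.6% |
| 10% | 0.5 | 0.6 / 0.8 | 19.06 / 18.92 | 87.2% / 87.7% |
| 10% | 1 | 0.6 / 0.8 | 18.90 / 18.62 | 87.7% / 88.7% |
| 20% | current model | – | 20.41 | 82.4% |
| 20% | 0.5 | 0.6 / 0.8 | 20.00 / 19.67 | 83.9% / 85.1% |
| 20% | 1 | 0.6 / 0.8 | 19.66 / 19.06 | 85.1% / 87.2% |

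Worked line (20%, q = 0.5, r = 0.6): 333.33 × (0.36/0.9 + 0.64/0.8) = 333.33 × 1.2 = 400, so SE = 20.00 and Φ(2.95 − 1.96) = 83.9%.

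At r = 0.3 the gain stays under 1 point: 82.4% to at most 83.1% at 20% missing. The q = 1 rows are upper limits, because patients lost before Week 6 usually have no Week 6 value. The 20% level is a reference point: SAP 4.2 uses it for adding patients only together with withdrawal above 25%.

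**4. Bias.** Suppose missingness depends on Week 6 change (assumed log-odds 0.5-1 per SD, r = 0.6-0.8, Week 6 effect 59 mL). The bias of the current model is 250 × r × the between-arm difference in mean standardised Week 6 residual among observed patients.

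| Pattern | 10% missing | 20% missing |
|---|---|---|
| Same rule in both arms | −0.8 to −3.3 mL | −1.3 to −5.3 mL |
| Rate 1.5 times higher on placebo | −3.0 to −7.1 mL | −5.9 to −13.5 mL |
| Rate 1.5 times higher on ensifentrine | +2.7 to +6.5 mL | +5.4 to +12.3 mL |

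That Week 6 data would remove this bias follows from the assumed mechanism; it is not evidence about this trial.

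**The case against.** **The imputation has other uses.** One might infer that it serves no purpose. The documents do not support that: the tipping-point analysis shifts the imputed values, and the subgroup analyses use the imputed data. The equivalence covers the overall difference only.

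**The match is not exact by rule.** Protocol 8.6.2.3 lets missed spirometry be collected later. SAP 6.4 would count such a 12-hour curve; the first item in SAP 16.1.4, read literally, might not. This stands as a small exception.

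**The SAP claims no independence.** It labels the item an observed-data analysis, and nowhere calls agreement reassuring. This stands, so the request is only for a sentence saying that a match is expected.

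**Stopping drug need not mean a missing curve.** A reader might infer that everyone on the combined phone and clinic option lacks Week 12 data. Patients who stop after Week 12 already have it. Before then, protocol 7.1 directs most of those who stop drug to the withdrawal assessments, and for withdrawals before Week 12 "every attempt should be made to have the patient complete the 12-hour spirometry procedures". Section 7.2 treats reduced follow-up as a fallback. The affected group is narrower and of unknown size.

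**The model follows protocol 9.4.1.** That section can be read as a baseline-only rule for this endpoint, and the same-parameter rule of SAP 16.2.2.1 applied to AUC0-12h would also give Week 12 only. This stands: the secondary method is an analogy, and the change is an improvement, not a correction. It does not reconcile 9.4.1 with 9.4.4 or the synopsis.

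**An open-ended list would loosen prespecification.** This is right, so the fix names one list.

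**Conclusion.** The point holds as a cheap improvement. As specified, the primary imputation repeats the observed-data ANCOVA for the overall treatment difference, within the limits above, and uses no other post-randomization FEV1. Equivalence follows from the models written in the SAP. The size of the gain rests on assumed correlations, missing shares and availability: about 0.6 to 1.1 power points at 10% missing and 1.5 to 2.7 at 20% missing when half of the missing patients have Week 6 FEV1. Bias is reduced only if dropout depends on earlier FEV1, mainly when it does so differently by arm.

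A reader might conclude that the primary analysis is invalid, or that its robustness is untested. Neither follows. The analysis is coherent under its stated missing-at-random assumption, and the opposite-arm, tipping-point, on-treatment and per-protocol analyses change the data or the assumptions. None of them uses the other-visit FEV1, however. The three protocol statements on imputation do differ and need aligning in any case.

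**What to change.** Before unblinding:

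1. In steps 1 and 2 of SAP 16.1.2, replace `<visits>` with one fixed list: average FEV1 AUC0-4h at Weeks 6, 12 and 24, plus AUC0-12h at Week 12.
2. Keep the current baseline-only imputation as a sensitivity analysis, as SAP 16.2.4 does for the key secondary lung-function endpoints. State that the first no-imputation analysis is expected to match it.
3. Align the synopsis and protocol 9.4.1 and 9.4.4 on one rule, and record the change in SAP 3.3.

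The cost is a short text edit and a longer variable list; no new data are needed. The change borrows across parameters, one step beyond SAP 16.2.2.1. Some off-drug values would be predicted partly from on-drug FEV1 under a treatment-policy estimand, which the SAP already accepts for the key secondary FEV1 endpoints. Week 24 values collected off drug partly offset this. A patient whose only post-dose FEV1 is from Day 1 gains nothing from this list.

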9.0 STATISTICAL CONSIDERATIONS

9.1 Statistical Hypotheses

The aim of this study is to show superiority of ensifentrine over placebo regarding selected efficacy measures. The null hypothesis to be tested for each endpoint will be that there is no difference between ensifentrine and placebo, against the alternative hypothesis that ensifentrine is better than placebo. All tests will be two-sided at a 5% significance level. Primary and key secondary endpoints used for claims will be tested in a sequential order to preserve the alpha level. Testing will stop once a not significant result is achieved. Test order will be FEV₁ AUC_{0-12h} at 12 weeks, peak FEV₁ at 12 weeks, weekly mean E-RS total symptom score at week 24, SGRQ total score at 24 weeks, morning trough FEV₁ at Week 12, FEV₁ AUC_{0-4h} at 12 weeks and proportion of SGRQ responders at Week 24.

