9.2 Sample Size Determination

Approximately 800 patients will be randomized. The standard deviation for the change in FEV₁ AUC_{0-12h} is estimated to be 250 mL. With a 2-sided test at a 5% significance level and 500 vs. 300 evaluable patients in the two groups, there will be an 90% power to detect a true difference of 59 mL between the treatments. If the withdrawal rate at 24 weeks exceeds 25% overall, additional patients may be randomized to the study to compensate for the loss of data.

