9.4.4 Missing Data

All data collected after treatment withdrawal will be used in the analyses. Patients withdrawn from study will perform an End-of-Study visit after decision to withdraw the patient has been made. Data collected at such visits will be used for analysis even if outside the visit window for the endpoint. Remaining missing data will primarily be imputed using multiple imputation based on baseline characteristics and data collected at post-randomization visits. In addition, a worst-case scenario using the average change in the opposite treatment group will be used for imputation as a sensitivity analysis. For the responder analysis of SGRQ, patients with no available data for imputation will be considered non-responders as a sensitivity analysis. In exacerbation analyses, patients are included with data collected up to last day in the treatment period/period of recording following treatment withdrawal.

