7.3. MISSING DATA

Missing safety data will not be imputed.

All data collected during the scheduled visits for patients on-treatment and off-treatment, for patients with treatment withdrawal, as well as the end-of-study visits for patients withdrawing from the study will be used for analysis performed on the mITT and that the remaining missing values will be handled as described in Sections 16.1.2, 16.2.2 and 16.3.2 of the SAP.

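### The opposite-arm average-imputation check in SAP 16.1.2 replaces observed off-treatment Week 12 values that the primary analysis keeps, so it mixes a change of data with a change of imputation rule

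*SAP*

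**What the plan says.** SAP 16.1.2 defines the check in one sentence: "Average imputation will be based on data collected on treatment at required visit, or at early termination visit". It works patient by patient. Where neither kind of value exists, the patient receives the mean change at that visit in the other randomized arm. SAP 16.2.2.4 and 16.2.4 carry the method to the key secondary endpoints by cross-reference.

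Other places set a different data rule:

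- Protocol 9.4.4: "All data collected after treatment withdrawal will be used in the analyses".
- Protocol 9.4.1 gives an order for the primary endpoint. Values from visits after treatment withdrawal, or from early-termination visits, are used first. Only where neither exists is a value imputed, by multiple imputation in the main analysis and by the opposite-arm mean in the worst-case check.
- SAP 7.3 says that "All data collected during the scheduled visits for patients on-treatment and off-treatment", together with end-of-study visits, enter the mITT analyses. It sends only what is still missing to 16.1.2.
- SAP 2.5 assigns a treatment-policy strategy to the primary estimand.

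SAP 3.3, which lists changes from the protocol, does not mention an on-treatment restriction.

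**The concern.** A check on missing-data handling should hold the observed data fixed and vary only how the gaps are filled. Here a Week 12 value observed off treatment does not meet the on-treatment condition. It is replaced by an early-termination value or, if there is none, by the opposite-arm mean. Protocol 7.1 to 7.2.1 ask sites to keep patients who stop drug in the study, and even the reduced schedule includes spirometry, so such values should exist.

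At stake is the interpretation of the protocol's own worst-case analysis. If it departs from the primary result, the departure could come from the assumption about missing values or from overwriting observed values that the estimand calls for. The check alone cannot tell the two apart.

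**Working it through.** **The plan's own figure.** Protocol 9.1 states: "All tests will be two-sided at a 5% significance level". Protocol 9.2 gives an SD that "is estimated to be 250 mL", "500 vs. 300 evaluable patients in the two groups", and "90% power to detect a true difference of 59 mL between the treatments".

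- SE = 250 × √(1/300 + 1/500) = 18.26 mL.
- Power = Φ(59/18.26 − 1.96) = 0.898, which reproduces the stated 90%. The difference detectable at exactly 90% is 59.2 mL.

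The data rule does not affect this figure. I use 59 mL only as a reference effect d.

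**Assumed quantities (not in the documents, taken as equal in both arms).**

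- m: share with no usable value at all.
- f: share with an off-treatment value at Week 12 and no early-termination value.
- ρ: share of the on-treatment effect d that persists off drug.

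The documents give only triggers for randomizing more patients. One is in Protocol 9.2 ("If the withdrawal rate at 24 weeks exceeds 25% overall"). SAP 4.2 adds a condition of more than 20% missing 12-hour data at Week 12. Neither is an estimate of f.

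**Nothing missing (m = 0).**

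- Treatment-policy difference = (1 − f + fρ) × d.
- Under the SAP wording, a share f in each arm takes the other arm's mean. The active mean becomes (1 − f)A + fP and the placebo mean (1 − f)P + fA, so the difference is (1 − 2f) × d.

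| f | Treatment policy, ρ = 0 to 1 (mL) | SAP check (mL) | Shift (mL) |
|---|---|---|---|
| 2% | 57.8 to 59.0 | 56.6 | 1.2 to 2.4 |
| 5% | 56.05 to 59.0 | 53.1 | 2.95 to 5.9 |
| 10% | 53.1 to 59.0 | 47.2 | 5.9 to 11.8 |

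The result moves although there is no missing value to make an assumption about.

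**With missing values.**

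- Protocol rule: (1 − 2m)/(1 − m) × [(1 − m − f) + fρ] × d.
- SAP wording: [1 − 2(m + f)] × d.
- With m = 10% and f = 5%, the protocol rule gives (0.80/0.90) × 0.85 × 59 = 44.6 mL at ρ = 0 and (0.80/0.90) × 0.90 × 59 = 47.2 mL at ρ = 1.
- The SAP wording gives 0.70 × 59 = 41.3 mL, so the gap is 3.3 to 5.9 mL.
- Over m = 5% to 20%, f = 2% to 10% and ρ = 0 to 1, the gap is 1.2 to 11.8 mL.

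**The other direction.** Protocol 7.1 asks patients who stop drug to complete the withdrawal assessments, and 7.3.1 asks that they stay on drug until that visit if possible. Suppose instead that 5% of each arm has both an on-drug early-termination value carrying the full effect and an off-treatment Week 12 value carrying none (ρ = 0). The check then gives 0.95 × 59 + 0.05 × 59 = 59.0 mL, against a treatment-policy value of 0.95 × 59 = 56.05 mL. The shift of 2.95 mL favours ensifentrine.

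**The case against.** The strongest reply is that SAP 7.3 governs. If all on- and off-treatment data enter first, 16.1.2 only ever sees values still missing, and the on-treatment phrase is a slip. That is possible, but the two sections then conflict and a programmer must choose. SAP 16.1.4 makes loose wording hard to assume: it separates an analysis of data collected whether or not on treatment from one limited to data collected while still on randomized treatment. It also already supplies an on-treatment analysis, so this check does not need the restriction.

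A reader might infer three stronger things, which the documents do not support:

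- *That all off-treatment data are lost.* Early-termination values carry no on-treatment condition, and Protocol 7.3.1.1 allows undosed serial spirometry at that visit. Only off-treatment values at the scheduled visit are at issue.
- *That the missing-data assumption goes untested.* Patients with no data still receive an opposite-arm value, and the tipping-point analysis in 16.1.2 stands separately.
- *That a discrepancy could never be explained.* For the primary endpoint, the two no-imputation analyses in 16.1.4 show the influence of off-treatment data apart from the opposite-arm rule. SAP 16.2.4 does not list that pair for the key secondary endpoints.

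It is also fair that f may be small. Under Protocol 7.2.2 patients return for spirometry only at Week 24 (and Week 48 in that stratum), 7.2.3 collects none, and COVID-positive patients leave the study. When the opposite-arm mean is the replacement, the shift is conservative for any ρ between 0 and 1; with nothing missing it would favour ensifentrine only if ρ were below −1. For the other spirometry endpoints, SAP 6.4 lets the end-of-study visit of a patient who left the study fill only a missing visit, so displacement of an observed value by an early-termination value is less likely there. These points limit the size; they do not remove the conflict.

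**Conclusion.** The concern holds for off-treatment values observed at the scheduled visit. As worded, the check departs from the protocol's order, from SAP 7.3 and from the treatment-policy estimand, without being declared as a change. Its result combines a different data set with a different imputation rule.

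At an assumed f = 5% with nothing missing, the unintended shift is about 3.0 to 5.9 mL against ensifentrine when the opposite-arm mean is substituted. It can run the other way when an on-drug early-termination value is substituted. These sizes rest on assumed f and ρ, equal in both arms, and on 59 mL as the on-treatment effect.

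It should not be inferred that the primary result is in doubt. The primary analysis, the testing order, the power, the tipping-point analysis and the observed-data analyses are untouched. This is a correction to one sensitivity analysis, worth making because it restores the worst-case check that the protocol describes.

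**What to change.** In SAP 16.1.2, remove the on-treatment condition so that the check accepts data collected at the required visit, on or off treatment, as well as early-termination data. State that the opposite-arm mean is applied only to patients whose value is imputed in the primary multiple imputation. Sections 16.2.2.4 and 16.2.4 then follow by cross-reference.

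If the restriction is intended, list it in SAP 3.3 and label the analysis as targeting a different estimand.

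The cost is one sentence and a change of input data set, made before unblinding. No new data are needed.
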